7.2.4 Discontinuation criteria based on LVEF

For asymptomatic subjects, if their LVEF is decreased by $\geq 20\%$ from baseline but not decreased to $< 50\%$ of baseline, they can still be treated with apatinib, but their LVEF should be reevaluated after 2 weeks at most. If LVEF is still decreased after reevaluation, apatinib should be interrupted. LVEF is evaluated every 2 weeks thereafter, and the subject can reduce one dose level to restart apatinib treatment after LVEF recovery. For such subjects, LVEF monitoring is still required in Week 2 (± 3 days) and Week 4 (± 3 days) after the administration is restarted, and LVEF monitoring should be performed every 4 weeks (± 3 days) thereafter.

If the LVEF value is below the lower limit of normal specified by the study site or drops to $< 50\%$, the subject should withdraw from the study. The LVEF should be continuously monitored every 4 weeks (± 3 days) thereafter until resolved or after at least 16 weeks of continuous monitoring.

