Grade I Hematological Toxicity	Maintain original dose		
Grade II Hematological Toxicity	Maintain original dose		
Grade III Hematological Toxicity	Interrupt treatment and give symptomatic treatment until toxicity returns to Grade \leq II, and then resume treatment at the original dose level	After treatment discontinuation during treatment cycle, hematological toxicity must recover to Grade \leq II before treatment can be resumed	At the beginning of the next cycle of administration, hematological toxicity must recover to Grade \leq II before treatment can be started
Grade IV Hematological Toxicity	Interrupt treatment and give symptomatic treatment until toxicity returns to Grade \leq II, and then resume treatment at the next lower dose level; upon complete recovery of toxicity, dose may be re-adjusted to the previous level to continue treatment; if a Grade IV hematological toxicity occurs again after such re-adjustment, dose should be reduced accordingly and no further adjustments shall be allowed		
Grade I Non-Hematological Toxicity	Maintain original dose		
Grade II Non-Hematological Toxicity	Give symptomatic treatment and continue study administration at the same time, if toxicity returns to Grade \leq I after one week, continue dosing; if the toxicity does not recover or even worsens, interrupt treatment until toxicity returns to Grade \leq I, and then resume treatment at the original dose level	After treatment discontinuation during treatment cycle, non-hematological toxicity must recover to Grade \leq I before treatment can be resumed	At the beginning of next cycle, non-hematological toxicity must recover to Grade \leq I before treatment can be started
Grade III Non-Hematological Toxicity	Interrupt treatment and give symptomatic treatment until toxicity returns to Grade \leq I, and then resume treatment at the original dose level, and reduce by 1 dose level for the next cycle; investigator may decide accordingly for certain patients based on the specific conditions without waiting for the next cycle; upon complete recovery of toxicity, dose may be re-adjusted to the previous level to continue treatment; if a Grade III non-hematological toxicity occurs again after such re-adjustment, dose should be reduced accordingly and no further adjustments shall be allowed		

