NCI Toxicity Grade	Regulations for Dose Modification	Regulations for Toxicity Recovery upon Re-Administration after Treatment Discontinuation	Regulations for Toxicity Recovery at the Beginning of Next Cycle
Grade IV Non-Hematological Toxicity	Interrupt treatment and give symptomatic treatment until toxicity returns to Grade \leq I, and then resume treatment at the next lower dose level for at least 1 cycle; upon complete recovery of toxicity, dose may be re-adjusted to the previous level to continue treatment; if a Grade IV non-hematological toxicity occurs again after such re-adjustment, dose should be reduced accordingly and no further adjustments shall be allowed (if a life-threatening adverse reaction, such as Grade IV renal impairment, neurotoxicity, cardiotoxicity, or hepatotoxicity occurs, discontinue the treatment and withdraw)		

ABBREVIATIONS AND DEFINITIONS

The following abbreviations and special terms are used in this study protocol

Abbreviations and Special Terms	Definitions
ACEI	Angiotensin converting enzyme inhibitor
AE	Adverse event
AFP	Alpha-Fetoprotein
AKP	Alkaline phosphatase
ALT	Alanine aminotransferase
ANC	Absolute neutrophil count
APTT	Activated partial thromboplastin time
ARB	Angiotensin II receptor blocker
AST	Aspartate aminotransferase
BUN	Blood urea nitrogen
B-Scan	B-mode ultrasound
Ca	Calcium
Cl	Chlorine
Cr	Creatinine
CR	Complete response
CT	Computed tomography
DCR	Disease control rate
DLT	Dose-limiting toxicity
DRQ	Data ready queue
ECOG PS	Eastern Cooperative Oncology Group Performance Status
eCRF	Electronic case report form
EGFR	Epidermal growth factor receptor
Fbg	Fibrinogen
GCP	Good Clinical Practice
FAS	Full analysis set
Glu	Glucose
Hb	Hemoglobin
HCC	Hepatocellular carcinoma
HFS	Hand-foot-skin reaction
HMG-CoA	β -Hydroxy β -methylglutaryl-coenzyme A
ITT	Intention to treat
K	Potassium
LD50	Median lethal dose
MRI	Magnetic resonance imaging
MTD	Maximum tolerated dose
Na	Sodium
NCI-CTC	National Cancer Institute Common Toxicity Criteria
OB	Occult blood
ORR	Objective response rate
OS	Overall survival
PD	Progressive disease
PDGFR	Platelet derived growth factor receptor
PFS	Progression free survival

Abbreviations and Special Terms	Definitions
PI	Principal investigator
PLT	Platelet
PR	Partial response
PRO	Protein
PPS	Per-protocol set
PT	Prothrombin time
q.d.	Quaque die
QoL	Quality of life
RBC	Red blood cell
RC	Red color sign
RECIST	Response evaluation criteria in solid tumors
RR	Response rate
RTKs	Receptor tyrosine kinase

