11. Women of childbearing potential must have a negative pregnancy test (serum or urine) within 7 days prior to enrollment, and be willing to take appropriate contraceptive measures during the trial and within 8 weeks after the last dose of the investigational drug. Male subjects should either undergo surgical sterilization, or agree to take

appropriate contraceptive measures during the trial and within 8 weeks after the last dose of the investigational drug;

12. Subjects must participate voluntarily, sign the informed consent form, have good compliance and corporate with follow-up visits.

3.3 Exclusion Criteria:

1. Patients who have received any local treatment within 4 weeks prior to participating in this study (including but not limited to surgery, radiation, hepatic artery embolization, TACE, hepatic arterial infusion, radiofrequency ablation, cryoablation, or percutaneous ethanol injection);
2. Patients with known intrahepatic cholangiocarcinoma, mixed hepatocellular carcinoma and fibrolamellar hepatocellular carcinoma; other uncured malignancies currently or within the past 5 years, except for cured skin basal cell carcinoma or cervical carcinoma in situ;
3. Patients planning to receive liver transplant (except for patients who have undergone liver transplant);
4. Patients with symptomatic ascites requiring therapeutic paracentesis or drainage, or with a Child-Pugh score > 2;
5. Patients with hypertension which cannot be controlled to the normal range by antihypertensives (systolic pressure > 140 mmHg, diastolic pressure > 90 mmHg);
6. Patients with Grade II or greater myocardial ischemia or myocardial infarction, uncontrolled arrhythmias (QTc interval \geq 450 ms in males and \geq 470 ms in females);
7. Patients with NYHA (see Appendix 5) Class III-IV cardiac insufficiency or LVEF (left ventricular ejection fraction) < 50% by echocardiography;
8. Presence of multiple factors affecting oral medications (such as inability to swallow, chronic diarrhea, and intestinal obstruction, which significantly affect drug administration and absorption);
9. Patients with a history of gastrointestinal bleeding within the past 6 months or a high risk of bleeding such as esophageal varices with bleeding risk, active ulcers, and fecal occult blood \geq (++); in the case of fecal occult blood (+), a gastroscopy is required;
10. Abdominal fistula, gastrointestinal perforation or abdominal abscess within 28 days prior to the study;

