11.1.3 Serious adverse event (SAE)

An SAE refers to a medical occurrence during the clinical trial that results in hospitalization, prolonged hospitalization, disability, incapacity, life threatening events or death, or congenital malformation. The following unexpected medical events are included:

- Events resulting in death;
- Life-threatening events (defined as events where the subject is at immediate risk of death at the time of the onset);
- Events resulting in hospitalization or prolonged hospitalization;
- Events resulting in permanent or serious disability/incapacity;
- Congenital anomalies or birth defects.
- Overdose.
- Pregnancy during the clinical trial.

Criteria for other SAEs specified in the protocol:

- Cardiac insufficiency - defined as any symptom or sign of reduced LVEF (NCI CTCAE Grade 3), or LVEF reduced by $\geq 20\%$ from baseline and below the lower limit of normal (or reduced to $< 50\%$).

- ALT $> 5 \times$ ULN and total bilirubin $> 2 \times$ ULN (such as direct bilirubin $> 35\%$; the bilirubin ratio should be measured).

Note: If possible, the bilirubin ratio assay should be completed. If the test cannot be performed due to limited capacity and the subject has reached the criteria of total bilirubin of $> 2 \times$ ULN, the event should be reported as an SAE.

Progressive disease

Progressive disease (including progressive signs and symptoms) should not be reported as an SAE. However, death due to progressive disease during the trial or safety reporting period should be reported as an SAE. Hospitalizations due to signs and symptoms of progressive disease should not be reported as an SAE. During the trial or safety reporting period, if the final outcome of the cancer is death, then the event leading to death should be reported as an SAE.

Other anti-tumor treatments

If a subject is to start another anti-tumor treatment, AEs except death will be reported until the start of the new anti-tumor treatment. Death that occurs within the SAE reporting period after study treatment is completed should be reported regardless of whether the patient received other treatment.

Hospitalization

During the trial, AEs resulting in hospitalization or prolonged hospitalization should be considered serious AEs. Any initial hospital admission by a medical facility meets this criterion (even if less than 24 hours).

Hospitalization does not include the following:

- Hospitalization at a rehabilitation institution

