11.3 SAE Reporting Procedures

Serious adverse events that occur starting from the signing of the informed consent form until 28 days (inclusive) after the last dose should be reported. Any SAE occurring during the trial must be immediately reported to the clinical research associate (CRA), the principal investigator, the PLA Tumor Center of the 81st Hospital of the Chinese People's Liberation Army and the Medical Director of Jiangsu Hengrui Pharmaceuticals Co., Ltd. via fax or phone. Meanwhile, the "New Drug Clinical Trial Serious Adverse Event (SAE) Report Form" should be completed, signed, dated, and submitted to NMPA within 24 hours.

During the continued treatment period, SAE should be reported to the sponsor within 24 hours. All information regarding the SAE should be documented in the SAE form. SAEs that occur during the continued treatment period until 28 days after the last dose should also be reported. SAEs that occur 28 days after the last dose are generally not reported unless suspected to be related to the investigational drug.

SAEs should be documented in detail, including symptoms, severity, date of onset, time of treatment, measures taken, time and method of follow-up, as well as outcome. If the investigator believes that an SAE is unrelated to the investigational drug but potentially related to study conditions (e.g., termination of the original treatment, or complications during the trial), then this relationship should be detailed in the SAE page of the case report form. If the severity of an ongoing SAE or its relationship to the investigational drug changes, a follow-up report of the SAE should be submitted to Jiangsu Hengrui Pharmaceuticals Co., Ltd. immediately. All SAEs should be followed until resolved or stabilized.

Table 13. Contact information of each institution

Institution	Contact	Telephone	Fax
National Medical Products Administration	Safety Supervision Department	[name]	[name]
PLA Tumor Center of the 81 st Hospital of the Chinese People's Liberation Army	[name] [name]	[name]	[name]
Jiangsu Hengrui Pharmaceuticals Co., Ltd.	[name]	[name]	[name]

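### Protocol 7.2.4 lets asymptomatic subjects continue apatinib at LVEF values where its next paragraph calls for withdrawal; secondarily, Table 8 allows a return from 250 to 500 mg that 7.2.3 bars

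*Protocol*

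**What the plan says.** **LVEF.** Protocol 7.2.4, paragraph 1, applies to asymptomatic subjects whose LVEF has fallen by at least 20% from baseline. If the value is not below 50% "of baseline, they can still be treated with apatinib, but their LVEF should be reevaluated after 2 weeks at most". If it is still decreased at that check, dosing is interrupted, and "the subject can reduce one dose level to restart apatinib treatment after LVEF recovery".

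Paragraph 2 begins "If the LVEF value is below the lower limit of normal specified by the study site or drops to" less than 50%, and says that the subject should then withdraw. It has no exception for asymptomatic subjects, and its 50% is not tied to baseline. Neither paragraph refers to the other.

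Exclusion criterion 7 (Protocol 3.3) rules out a baseline LVEF below 50%. Protocol 11.1.3, repeated in SAP 4.1, defines a cardiac SAE that includes an LVEF reduced by at least 20% "from baseline and below the lower limit of normal (or reduced to" less than 50%). Here too the 50% is not tied to baseline.

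**Dose.** Protocol 7.1 sets three levels: 750, 500 and 250 mg. Protocol 7.2.3 allows at most two reductions and says that the dose may not go back up once the third level is reached. Table 8 in 7.1 shows, in tablets of 250 mg, the sequence 3-2-3-2-1-2-1.

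**The concern.** These are operative stopping and dosing rules, and a site needs one answer from them. Take an asymptomatic subject with a baseline LVEF of 60% who is now at 45%. With the 20% read as relative, paragraph 1 permits further apatinib and paragraph 2 calls for withdrawal.

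A site that follows paragraph 1 could dose for up to two weeks before re-evaluation. After recovery it could restart, one level lower, a subject whom paragraph 2 would have withdrawn. SAP Appendix 1 grades failure to discontinue a subject who meets a withdrawal criterion as a critical deviation. A site could therefore incur one while following the protocol's own text.

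On dose, a site that follows Table 8 doubles the daily dose of a subject whom 7.2.3 holds at 250 mg.

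**Working it through.** The plan states no figure here to reproduce. The check compares the two LVEF ranges and then reads Table 8 against 7.2.3.

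**Inputs.** Baseline *b* is at least 50% (3.3, criterion 7). The continue rule and the withdrawal rule come from 7.2.4. The site LLN is not given.

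**Formulas.**
- Continue range: 0.5*b* to 0.8*b* if the 20% is relative, or 0.5*b* to *b* − 20 if it means percentage points. The text does not say which.
- Withdrawal range: LVEF below *T*, where *T* is the larger of 50% and the site LLN.
- Overlap: from 0.5*b* up to the smaller of the continue limit and *T*.

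**Results with *T* = 50% (LVEF in %).**

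| Baseline | Continue range, relative | Part in withdrawal range | Continue range, points | Part in withdrawal range |
|---|---|---|---|---|
| 50 | 25–40 | all | 25–30 | all |
| 55 | 27.5–44 | all | 27.5–35 | all |
| 60 | 30–48 | all | 30–40 | all |
| 65 | 32.5–52 | 17.5/19.5 = 90% | 32.5–45 | all |
| 70 | 35–56 | 15/21 = 71% | 35–50 | all but the end point 50 |
| 75 | 37.5–60 | 12.5/22.5 = 56% | 37.5–55 | 12.5/17.5 = 71% |

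The whole continue range is in conflict when 0.8*b* < 50, so *b* < 62.5%, or when *b* − 20 < 50, so *b* < 70%. If a site's LLN were 55% (an assumption), these limits would rise to 55/0.8 = 68.75% and 55 + 20 = 75%.

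**Worked cases at baseline 60%.** At 45%, the fall is 15/60 = 25% and the value is 45/60 = 75% of baseline, so both paragraphs apply on the relative reading. At 38%, the fall is 22 points and the value is 38/60 = 63% of baseline, so both apply on either reading.

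**SAE criterion.** Every value in the overlap has fallen by at least 20% and is below the LLN or below 50%. Both parts of the criterion in 11.1.3 are therefore met throughout.

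**Table 8.** The sequence 3-2-3-2-1-2-1 has six steps. The fifth, from one tablet to two (250 to 500 mg), is the return that 7.2.3 forbids from the third level. Without the last two rows the sequence is 3-2-3-2-1. That still contains three downward steps against the two reductions in 7.2.3, so the count needs a definition. The synopsis and 4.5.2 call 500 mg the first reduction and 250 mg the second, and 7.2.5 uses the ladder 750-500-250-withdrawal. The natural meaning is therefore two dose levels below 750 mg.

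**Dose intensity.** SAP Appendix 3 divides cumulative dose by duration and compares the result with 750 mg/day. On the days affected, 250 mg gives 250/750 = 33% and 500 mg gives 500/750 = 67%.

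**The case against.** The strongest reply is that paragraph 1 is only a permission and paragraph 2 is a stop rule. A site that withdraws the subject breaches neither. The section is headed as discontinuation criteria, and the critical grading in SAP Appendix 1 also favours the stop rule. The words *of baseline* look like a drafting or translation slip, because 11.1.3 and SAP 4.1 use 50% without them.

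There are other safeguards. The Regulations for Dose Modification table interrupts dosing for Grade III non-hematological toxicity. For Grade II, after one week, "if the toxicity does not recover or even worsens, interrupt treatment until toxicity returns to Grade" I or lower. For life-threatening reactions at Grade IV, "such as Grade IV renal impairment, neurotoxicity, cardiotoxicity, or hepatotoxicity occurs, discontinue the treatment and withdraw". Protocol 11.3 adds: "Any SAE occurring during the trial must be immediately reported to the clinical research associate (CRA), the principal investigator" and others. The investigator may also withdraw any subject (3.4). Few cases would come to light, since echocardiography after screening is prompted only by clinically significant ECG abnormalities (Schedule of Activities, note f; 9.2).

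Most of this stands and limits the weight of the point, but it does not remove the conflict. Paragraph 1 is the narrower rule, with its own steps for re-evaluation, interruption and restart, so a site could reasonably read it as the exception. Reading paragraph 2's 50% as relative to baseline would still leave its LLN trigger. SAE reporting does not stop dosing. The documents give no CTCAE cut-offs for LVEF, so the reach of the toxicity table cannot be established from them.

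On dose, note a to Table 8 generally allows a return to the previous level after full recovery, which supports the disputed row. The bar in 7.2.3 is specific to the third level, so the protocol holds two rules.

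A reader might also infer that 7.1, which allows no modification after a repeat reduction, bars Table 8's step from 500 to 250 mg. The context does not support that. The same section allows two levels of reduction, and 7.2, 7.2.3 and note b to Table 8 state the limit as not raising the dose again.

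**Conclusion.** The point holds as a wording conflict in safety rules that should be fixed. On the current text, permission to continue and the call to withdraw overlap at every baseline checked from 50% to 75%, on both readings of the 20%. Below 62.5% (relative) or 70% (points), no part of the continue range is free of conflict, taking the threshold as 50%. A higher site LLN widens the conflict. The 250 to 500 mg step in Table 8 contradicts 7.2.3.

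Two stronger inferences are not supported. One is that the protocol requires dosing through a cardiac SAE: it permits dosing in one paragraph and calls for withdrawal in the next. The other is that many subjects are at risk: the number is unknown and, given how seldom LVEF is measured on study, probably small.

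The OS sample size and primary test are unaffected. Dose intensity under SAP Appendix 3 would change for any subject dosed under the conflicting rules.

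**What to change.** **Protocol 7.2.4.**
- In paragraph 1, delete *of baseline* and add *and not below the site's lower limit of normal*.
- State whether the 20% is relative or in percentage points.
- Add that paragraph 2 takes precedence, so that restart after recovery applies only to subjects who never met the withdrawal rule.

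The continue rule then operates only from a baseline of 62.5% (relative) or 70% (points) upward, or higher where the site LLN exceeds 50%.

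**Table 8 and 7.2.3.** Delete the last two rows of Table 8, leaving 3-2-3-2-1. State in 7.2.3 that *two dose reductions* means two dose levels below 750 mg.

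**Optional.** In 7.1 and the Regulations for Dose Modification table, say that after a repeat reduction the dose may be lowered further but not raised.

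**Cost.** Edits to 7.2.4, two table rows and one clause in 7.2.3, plus the ethics committee approval or filing under Section 15 and a letter to sites. No new visits or procedures are needed.

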7.2.5 Discontinuation criteria based on prolonged QT interval

1) If the patient's ECG shows QTcF > 480 ms, the use of apatinib should be interrupted, and the following measures should be immediately taken:

- (1) Immediately notify the sponsor, safety monitoring committee or scientific committee;
- (2) Analyze serum potassium and magnesium, and if it is lower than the lower limit of normal, use supplements to correct serum potassium and magnesium to within the normal range;
- (3) The concomitant medication must be reviewed;
- (4) The use of apatinib and the compliance with the dose must be verified;
- (5) Perform an ECG examination within 1 h after the first episode of QTcF > 480 ms;
- (6) If QTcF is still > 480 ms, repeat the ECG examinations at least once a day when clinically needed, until QTcF is < 480 ms;
- (7) If QTcF is still > 480 ms in repeated measurements and lasts for more than 2 weeks, apatinib treatment must be discontinued.

2) Guidelines for resuming drug administration:

- (1) If the cause of QTcF prolongation (except apatinib) is determined, and if QTcF returns to < 450 ms within 2 weeks after correction and is within 20 ms of the baseline value, apatinib treatment can be resumed at the same dose;

(2) If the cause of QTcF prolongation cannot be determined, and if QTcF returns to < 450 ms within 2 weeks and is within 20 ms of the baseline value, apatinib treatment can be resumed at the same dose;

(3) If QTcF exceeds 480 ms again after the subject is exposed to the investigational drug again, the use of the investigational drug should be discontinued;

(4) After the subject is exposed to the investigational drug again, if QTcF is prolonged by more than 20 ms from baseline or is between 450 and 480 ms and lasts for more than 2 weeks, the dose of the investigational drug should be modified as follows:

- Reduced from apatinib, 750 mg, q.d. to apatinib, 500 mg, q.d.;
- Reduced from apatinib, 500 mg, q.d. to apatinib, 250 mg, q.d.;
- Withdrawal.

7.2.6 Discontinuation criteria based on liver function

1) If the subject has $ALT > 5 \times ULN$ and total bilirubin $> 2 \times ULN$, the following measures must be taken:

(1) Immediately discontinue the use of the investigational drug and give active symptomatic treatments;

(2) Complete the SAE form and handle it in accordance with the requirements for SAE in Section 11 of this protocol;

(3) Follow-up the event according to the requirements for "Follow-up of Adverse Events" in Section 4 of this protocol, and check liver function every week until it returns to the baseline level;

7.3 If the subject experiences any of the following conditions:

$ALT > 8 \times ULN$ or $ALT > 5 \times ULN$ for more than 2 weeks: The patient must be reexamined within 3 days after the first occurrence of the event, and then reexamined weekly to monitor whether the ALT value continues to increase. If the ALT value continues to increase, the use of the apatinib should be interrupted. The liver function should be reexamined within 2 weeks. If the treatment is effective and the subject is willing to continue to receive the apatinib treatment after obtaining the results of the liver function test, the subject can resume the apatinib treatment at the next lower dose level after obtaining the permission of the investigator and the medical director of the sponsor, and the liver function of the patient should be monitored every 2 weeks until it returns to the baseline level.

Other rules

To ensure the consistency of dose modifications throughout the study, treatment should be first discontinued before undergoing a dose modification for each dose cycle. The dose can only be reduced if the subject still cannot tolerate the dose after dose interruption.

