9.2 Treatment Period

- Check the blood pressure once a week post-administration. If the blood pressure is abnormal, follow up with the blood pressure every day, and check the blood pressure three times a week for two cycles after the blood pressure returns to normal, and once a week thereafter.
- Within the first two cycles of administration, carry out the following examinations every two weeks (± 3 days, except for statutory holidays): hematology, urinalysis (not required for female subjects during their menstrual period), hepatic and renal function, and electrolytes. From Cycle 3, the examination is carried out once only at the end of each cycle (± 3 days, except for statutory holidays).
- Within the first three cycles of administration, a 12-Lead ECG is carried out at the end of each cycle (± 3 days, except for statutory holidays), and then carried out at the end of every two cycles (± 7 days, except for statutory holidays). Each examination is carried out after administration for 3 times with about 5 min apart and QTc interval indicated. If there are symptoms such as precordial pain and palpitations, the myocardial zymogram (creatinine kinase, lactate dehydrogenase) should be tested immediately, and ECG should be performed at any time. For clinically significant ECG abnormalities, echocardiography (LVEF) should be performed.
- Physical examination, vital signs, PS score, and coagulation function tests are performed every cycle (± 3 days, except for statutory holidays).
- CT or MRI examination and objective efficacy evaluation of tumor are performed once at the end of every two cycles (± 7 days, except for statutory holidays). If the efficacy reaches CR, PR or SD, the subject must be reexamined 4 weeks after the first evaluation.

Note: For subjects who withdraw from the trial due to unacceptable toxicity, the efficacy evaluation should be conducted upon withdrawal if the efficacy evaluation is not carried out within 4 weeks before withdrawal. Thereafter, the imaging examination is performed at the same frequency, i.e., every 2 cycles until PD or use of other anti-tumor treatments. The radiographic evidence of PD of these subjects must be obtained.

- The quality of life score must be evaluated before each objective efficacy evaluation of tumor.
- Serum AFP is tested once at the end of Cycle 2 (± 7 days, except for statutory holidays) and at the end of Cycle 5 (± 7 days, except for statutory holidays). There is no strict requirement after Cycle 5.

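### For an isolated high ALT, Protocol 7.2.6 and the dose-modification table differ on interruption and restart, and neither document says which governs

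*Protocol*

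**What the plan says.** Two parts of the protocol cover the same patient.

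**Section 7.2.6** (the second item, numbered 7.3 in the text) applies to ALT above 8 x ULN, or above 5 x ULN for more than two weeks. ALT above 5 x ULN together with bilirubin above 2 x ULN falls under the first item of 7.2.6 and stops treatment at once, so only isolated ALT elevation is at issue here. ALT is retested within 3 days and then weekly, and "If the ALT value continues to increase, the use of the apatinib should be interrupted". Restart carries the condition "If the treatment is effective and the subject is willing to continue to receive the apatinib treatment", once a liver test result is available. Then "the subject can resume the apatinib treatment at the next lower dose level after obtaining the permission of the investigator and the medical director"; the director meant is the sponsor's. Liver function is then followed every two weeks until it is back at baseline.

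**The Regulations for Dose Modification table**, placed after the schedule of activities, works by toxicity grade. Grade III and IV non-hematological toxicity is interrupted. Grade II gets a week of symptomatic treatment, and "if the toxicity does not recover or even worsens, interrupt treatment until toxicity returns to Grade" I or less. Two further columns apply to all non-hematological toxicity: "After treatment discontinuation during treatment cycle, non-hematological toxicity must recover to Grade" I or less, and "At the beginning of next cycle, non-hematological toxicity must recover to Grade" I or less. Life-threatening Grade IV hepatotoxicity leads to withdrawal.

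**Monitoring (section 9.2):** "Within the first two cycles of administration, carry out the following examinations every two weeks"; after that, "From Cycle 3, the examination is carried out once only at the end of each cycle".

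**The concern.** The ALT-specific rule is looser than the general table on interruption and recovery, and stricter than the Grade III row on restart dose. A site that takes 7.2.6 as governing could keep dosing while ALT sits on a plateau above 8 x ULN, or restart before the liver injury has resolved. A site that works from the table would do neither.

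What is at stake is patient safety and uniform dosing across sites, in a population with little hepatic reserve. Section 3.2 admits patients with ALT just under 5 x ULN and with a Child-Pugh score of 7.

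**Working it through.** There is no plan figure to reproduce. The check compares the two rules.

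**Assumption.** Grading is by NCI-CTCAE 4.0 (section 11.2), but the documents do not print the ALT cut-offs. I assume only that ALT above 5 x ULN is worse than Grade I, and test each higher grade in turn.

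| If the ALT value is | Table: interrupt | 7.2.6: interrupt | Table: restart level | 7.2.6: restart level | Table: restart dose | 7.2.6: restart dose |
|---|---|---|---|---|---|---|
| Grade II | after 1 week without recovery | only on a further rise | Grade I or less | none given | original | next lower |
| Grade III | at once | only on a further rise | Grade I or less | none given | original, one level down next cycle | next lower |
| Grade IV | at once; withdraw if life-threatening | only on a further rise | Grade I or less | none given | next lower | next lower |

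The instructions on interruption and recovery differ in every row, so the finding does not depend on the exact grade mapping.

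**Days from detection to interruption.**
- Table: 0 (Grade III or IV) or 7 (Grade II unresolved).
- 7.2.6, above 8 x ULN: at the retest within 3 days or later, and only if rising.
- 7.2.6, above 5 x ULN: more than 14, and only if rising.

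**Scheduled liver tests**, allowing each visit its 3-day window either way:
- Cycles 1 and 2: 14 days apart, range 14 − 6 = 8 to 14 + 6 = 20.
- From Cycle 3: 28 days apart, range 28 − 6 = 22 to 28 + 6 = 34.

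Take ALT of 6 x ULN first seen at the end of Cycle 3. Under the table, Cycle 4 may not start. Under 7.2.6 neither trigger is met yet, so it asks for nothing, and the next scheduled test is about 28 days away.

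**Restart.** The neighbouring rules ask for recovery: the QTcF rule in 7.2.5 gives a number, and the LVEF rule in 7.2.4 requires recovery without one. The ALT rule states neither. Its effectiveness condition may mean that apatinib is working or that the liver treatment worked, and neither reading supplies an ALT level. The two-weekly follow-up until baseline shows that restart before baseline is foreseen. It does not by itself show that restart above Grade I is intended.

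**Precedence.** Section 7.2 introduces its subsections as the specific rules, which could lead a site to rank 7.2.6 above the table. Section 7.2.1, under the same introduction, ties interruption and reduction to Grade II or higher non-hematological toxicity. It exempts only controllable nausea and vomiting and low fever with a clear cause; ALT is not named. The closing paragraph of 7.2.6 puts interruption before dose reduction and does not settle the order either. Neither document contains a precedence statement.

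**Rough frequency (section 1.5.7, Table 6).** Grade III–V transaminase increase, exact (Clopper-Pearson) 95% intervals:
- 750 mg: 7/51 = 13.7% (5.7% to 26.3%).
- Both doses: (7 + 8)/(51 + 70) = 15/121 = 12.4% (7.1% to 19.6%).

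These counts pool ALT with AST and give no level, duration, trend or accompanying bilirubin.

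**The case against.** The strongest reply is that these rules add to each other and do not conflict. Section 7.2.6 never tells a site to continue dosing on a stable high ALT and never permits restart above Grade I. The table's recovery columns are mandatory and carry no ALT exception, and 7.2.1 puts the grade-based scheme inside 7.2 itself. A site can apply the table and add the retests and permissions from 7.2.6, so the restart level missing from one text is supplied by the other. The Cycle 3 example leads to harm only if the mandatory next-cycle rule is ignored, and applying the two-week trigger on time already calls for an earlier repeat test.

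Much of this stands. A reader might infer that the protocol instructs sites to dose through liver injury. The documents do not support that: continued dosing is implied and not stated, because an interruption that depends on a further rise makes sense only for a patient still taking the drug. Several safeguards also limit the harm: the immediate stop for a combined ALT and bilirubin rise, withdrawal for life-threatening Grade IV hepatotoxicity, the investigator's right to withdraw a subject (section 3.4), and two permissions before restart.

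Two things remain. Nothing tells a site to choose the table. And following the table does not resolve the Grade III restart dose, where the two texts expressly differ. The Grade III row softens this by letting the investigator reduce without waiting for the next cycle, but that is a discretion, whereas 7.2.6 fixes the lower level.

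**Conclusion.** The point holds and should be fixed. For isolated ALT elevation in the stated range, the two texts give different instructions on interruption and recovery, contradict each other expressly on the Grade III restart dose, and leave precedence open. On interruption and recovery the risk is confined to sites that read 7.2.6 as the overriding specific rule.

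The number of patients affected is unknown. A reader might take the phase II figure of 13.7% as the share at risk, but the documents do not support that. Some of those patients may also have had a bilirubin rise that triggers the immediate stop: Grade III–V bilirubin increase was 8/51 = 15.7% at the same dose, with the overlap not reported. Nor do the documents support inferring an effect on the OS analysis, and none is claimed. The conclusion rests on one assumption, that ALT above 5 x ULN is worse than Grade I.

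**What to change.** Amend the isolated-ALT item of 7.2.6 as follows:

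1. State that the table's interruption and recovery requirements also apply to isolated ALT elevation, in addition to the 3-day and weekly retests and the two permissions.
2. Delete the condition that ALT must continue to increase before treatment is interrupted.
3. State that restart after such an event is at the next lower dose level, and cross-refer to this from the Grade III row of the table.

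Because patients may enter with ALT just under 5 x ULN, the medical team should confirm whether return to baseline may replace Grade I for those already above Grade I at entry.

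The cost is one amendment, with ethics approval or filing under section 15, and a note to sites. Expect somewhat more interruption, lower dose intensity and a few extra liver tests. Some recoveries may exceed the two-week interruption limit in 7.2.2, a breach that SAP Appendix 1 grades as Critical, so the team should expect such cases.
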